# Background

More than 1.3% of Americans, including over 150,000 children, suffer from severe physical impairments (SPI) that impede their ability to communicate. Over 500,000 of these individuals are adults and children with SPI who require augmentative and alternative communication (AAC) technology to be able to express themselves. These include a wide range of technologies and methods ranging from sign language and gestures to hi-tech speech-generating devices. However, many individuals with SPI lack the manual dexterity required to operate these assistive technologies and, as a result, require an alternative means of computer access such as head-or eye-tracking. Even then, these alternative access methods are often too tedious for individuals with SPI, as they require frequent recalibrations and readjustments to accommodate changes in disease progression, body position, and/or environment. It is therefore not uncommon that prospective users invest weeks or months of training time into using these devices, only to achieve inconsistent or inaccurate performance that impedes effective and intuitive communication. There is an urgent need to develop turnkey AAC devices that are able to automatically accommodate the unique physical access needs of individuals with SPI.

## Goal of the Overall Study

Our team of experts in wearable sensor systems, algorithms, and human machine interfaces at Altec, Inc., in collaboration with a team of speech researchers and clinicians from Boston University ([name] Lab) and Madonna Rehabilitation Hospital's Institute for Rehabilitation Science & Engineer (Communication Center Lab), aims to develop a more reliable, portable, and intuitive AAC device for individuals with SPI. This device will leverage direct recordings of head movement and facial muscle contractions from a combined surface electromyographic (sEMG) and inertial measurement unit (IMU) sensor to provide a means for controlling cursor movements and selection on an individualized keyboard interface that allows to adapt the device to the unique residual motor function of each user for improved communication capabilities. Through this innovation, we aim to provide individualized AAC solutions to all individuals – including those with the most complex needs – to preserve the fundamental human right of communication.

This work is a continuation of pilot studies by our team over the past 4 years, which have focused on the development of sensor-based access methods and adaptive interfaces that shift the burden of learning from the patients to the device. Since sEMG and IMU signals directly measure muscle control and body kinematics, such as occurs to produce head movement, they provide a reliable, portable, and intuitive means to adapt the device to the unique residual motor function of each user.

## **Specific Aims**

A series of experiments will be performed where control subjects and participants with SPI will be asked to perform head movements and eyeblinks to control the movement of a cursor and the selection of targets on a computer or tablet screen while IMU and sEMG signals are recorded from a sensor placed on the participants' forehead. These experiments will demonstrate that a novel sEMG/IMU-based access method is uniquely capable of characterizing subject-specific variations in movement capabilities in a heterogeneous sample of individuals with SPI to inform the adaptation of an AAC keyboard interface that accommodates residual motor function unique to each user. Specifically, sEMG and IMU signals during head movement and eyeblinks will be translated into repeatable cursor control and target selection that replicate subject-specific movement capabilities. This information will be used to adapt the configuration, orientation, and layout of an AAC orthographic keyboard interface to accommodate the head movement characteristics unique to each subject. The newly developed sEMG/IMU-based models and personalized keyboard interface will be tested to demonstrate that this new access method improves AAC performance when compared to communicating on a generic cursor-to-text AAC interface that uses the same configuration but is not optimized for the individual.

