# Protocol

The experiments require the subjects to utilize head motion to move a cursor on a computer or tablet screen interface. These interfaces will be of two general kinds: an interface that affords us the opportunity to assess generic cursor sensor control for targets located at different orientations and distances; and an orthographic interface where letters are arranged in either a standard (QWERTY) keyboard configuration or an optimized configuration specific to their individual control capabilities. During all experiments, participants will be seated in front of a monitor or tablet and asked to move a cursor appearing on the screen based on data extracted from a wireless Trigno Avanti (Delsys, Inc.) sensor worn on their forehead. When the cursor reaches the target, the subject must select the target by contracting their facial muscle (i.e.: via sEMG signals from either eye blinking or raising their eyebrows).

In some tasks, letters will be highlighted in the appropriate sequence to spell words presented to the subject. The selection and capture of the targets by the subject will be achieved by blinking or raising their eyebrow while the cursor is hovering at or near the target. In other tasks, participants will be asked to spell a series of words presented to them on the computer interface by moving the cursor with the aid of the head mounted IMU and select the target with the aid of the measured sEMG activity. The number of sentences will be arranged in consultation with our clinical collaborators so that the procedures can be completed within a reasonable timeframe.

Additional data acquisition during these experiments may include standard video recordings to assist in post-processing interpretation of results; and user-rated report of fatigue, effort, perceived benefit, ease of use or satisfaction through a brief Likert-type questionnaire.

Each session should require 1-3 hours over 1-2 sessions (depending on subject stamina) with rest periods provided at least every 10 minutes to avoid fatigue or lack of attentiveness.

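### Does the aim promise an access-method effect that the individualized-versus-QWERTY comparison cannot show?

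*Combined protocol and SAP*

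**What the plan says.** The Specific Aims section announces a test that will "demonstrate that this new access method improves AAC performance when compared to communicating on a generic cursor-to-text AAC interface" and describes the comparator as an "interface that uses the same configuration but is not optimized for the individual". The subject of that sentence is the newly built sensor models together with the personalized keyboard. Earlier in the same section the plan states that "a novel sEMG/IMU-based access method is uniquely capable of characterizing subject-specific variations in movement capabilities", and then: "This information will be used to adapt the configuration, orientation, and layout of an AAC orthographic keyboard interface".

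Under the Protocol heading, participants move "a cursor appearing on the screen based on data extracted from a wireless Trigno Avanti (Delsys, Inc.) sensor worn on their forehead"; this applies to all experiments, and targets are selected by facial sEMG. In the orthographic interface, "letters are arranged in either a standard (QWERTY) keyboard configuration or an optimized configuration specific to their individual control capabilities".

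The data analysis text, which follows the Alternatives to Participation heading, states the comparison as individualized against generic (QWERTY) keyboard. Each device is measured within one session. QWERTY goes in the second session (Day 2), as a reference, because QWERTY is widely familiar and participants will by then know the sensor control. Results are summarized as mean and standard deviation per metric for each participant across the two conditions. The same text describes the analyses as serving prototype work and early development, not proof of efficacy.

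**The concern.** Three things look wrong on a first reading.

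- **Attribution.** The documents mostly use access method for the sensor control. The Background speaks of users who "require an alternative means of computer access such as head-or eye-tracking", and the closing list of outputs names the access method and the individualized keyboards separately. An aim that credits improvement to the access method then seems to promise a comparison with other access technology. None is planned.
- **Same configuration.** The comparator is said to share the configuration, yet configuration is among the things adapted, and the Protocol section calls QWERTY and the optimized layout different configurations.
- **Confounding.** The one contrast available, individualized versus QWERTY, coincides with a fixed session order and with prior QWERTY familiarity.

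At stake is the conclusion. A gain could be credited to the sensor when only the keyboard differed, or a null result could be read as failed personalization when practice or familiarity had helped QWERTY.

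**Working it through.** The documents give no sample size, effect size or standard deviation for this comparison, so there is no figure to reproduce. The check concerns what the two conditions can identify.

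**Inputs**

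- Access: forehead sensor in all experiments (Protocol).
- Keyboard: QWERTY or individually optimized (Protocol).
- Sessions: one per device, QWERTY in the second (data analysis text).
- Position of the individualized keyboard: not stated. The Protocol section speaks of 1-2 sessions; the inclusion criteria for individuals with SPI ask for availability for at least 3-4.

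**Step 1: estimability.** Suppose the individualized keyboard comes first, which is an inference. With columns for intercept, sensor access, individualized keyboard and session 2, the rows are:

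- individualized: [1, 1, 1, 0]
- QWERTY: [1, 1, 0, 1]

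The rank is 2 for 4 terms. The access column equals the intercept column, so an access effect is not estimable. Subtracting the rows gives [0, 0, 1, -1]: only keyboard minus session is estimable. A fifth column for QWERTY familiarity leaves the rank at 2.

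**Step 2: which contrast is planned.** The Specific Aims sentence tests models plus personalized keyboard against an interface not optimized for the individual. The data analysis text tests individualized against QWERTY. Both name the same contrast. Same configuration contradicts the rest only if it means letter layout; if it means the sensor and cursor set-up, it agrees with the Protocol section.

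**Step 3: direction of a session effect.** Let K be the true keyboard benefit, S the change from earlier to later session (practice positive, fatigue negative) and F the advantage from QWERTY familiarity. The observed difference, individualized minus QWERTY, is K - S - F if the individualized keyboard comes first and K + S - F if it comes after. The values below are assumptions in arbitrary units: S from -10 to +20, F from 0 to 10.

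| Order | K | Highest difference | Lowest difference |
|---|---|---|---|
| Individualized first | 0 | 0 + 10 - 0 = +10 | 0 - 20 - 10 = -30 |
| Individualized first | 10 | 10 + 10 - 0 = +20 | 10 - 20 - 10 = -20 |
| Individualized after | 0 | 0 + 20 - 0 = +20 | 0 - 10 - 10 = -20 |
| Individualized after | 10 | 10 + 20 - 0 = +30 | 10 - 10 - 10 = -10 |

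With no true benefit, a positive difference is possible under either order. A rule that discounts only null or negative results is therefore unsound.

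**Step 4: what each remedy would gain.**

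- *Rewording the aim* to name individualized versus QWERTY leaves every planned summary as it is.
- *A limitation sentence* leaves the rank at 2.
- *Splitting by task type* relies on the statement that "In some tasks, letters will be highlighted in the appropriate sequence to spell words presented to the subject". The documents do not say that highlighted and free spelling tasks are both run on both keyboards, and a split would leave fewer trials behind each mean and standard deviation.
- *Varying the order across participants* would raise intercept, keyboard and session to rank 3 of 3 when participants are pooled. All five columns would reach only rank 3 of 5, with access and familiarity still not separable. Within one participant, with one session per keyboard, the rank stays at 2, and the participant is the unit at which this plan evaluates change. It would also give up the stated reason for placing QWERTY second.

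**The case for a change.** The best case for a change is that an aim should match its analysis, and that the cost is a few words. The term access method does refer to the sensor in most places, so a reader coming from the Background could take the aim as a claim against head- or eye-tracking. Verbs such as demonstrate and validate are stronger than the early-development purpose supports. The data analysis text explains why QWERTY is the reference but not how a null result should be read.

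Much of this is accurate. The wording is loose, and keyboard is tied to session. But no rival access technology is named as comparator anywhere, and the text that governs the analysis has the contrast right, so an analyst following it would not estimate the wrong thing. QWERTY familiarity is disclosed and is the stated reason for the choice, so it may belong to the intended comparator and need not count as bias. The argument that practice would mainly favour QWERTY depends on the individualized keyboard coming first, which the documents do not say.

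**Conclusion.** No change to the plan follows. The access-method point is a slip of wording in one sentence; the planned contrast is individualized versus QWERTY keyboard, both under sensor control, and it is stated correctly where the analysis is described.

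The confounding of keyboard with session is real: rank 2 for 4 terms, with only their combination estimable. It is a trade-off that the plan makes openly, to measure a familiar reference keyboard once participants know the sensor control, in descriptive single-subject work. Its size cannot be derived from the documents and its direction is unknown. An analyst reporting these results would sensibly describe any difference, positive or null, as that between the keyboards in the order used, and would make no claim about the sensor.

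This conclusion assumes that the comparison stays descriptive and at the early-development level that the plan states. If the same data were offered as evidence of efficacy, the fixed order would matter much more.

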# Protocol

The experiments require the subjects to utilize head motion to move a cursor on a computer or tablet screen interface. These interfaces will be of two general kinds: an interface that affords us the opportunity to assess generic cursor sensor control for targets located at different orientations and distances; and an orthographic interface where letters are arranged in either a standard (QWERTY) keyboard configuration or an optimized configuration specific to their individual control capabilities. During all experiments, participants will be seated in front of a monitor or tablet and asked to move a cursor appearing on the screen based on data extracted from a wireless Trigno Avanti (Delsys, Inc.) sensor worn on their forehead. When the cursor reaches the target, the subject must select the target by contracting their facial muscle (i.e.: via sEMG signals from either eye blinking or raising their eyebrows).

In some tasks, letters will be highlighted in the appropriate sequence to spell words presented to the subject. The selection and capture of the targets by the subject will be achieved by blinking or raising their eyebrow while the cursor is hovering at or near the target. In other tasks, participants will be asked to spell a series of words presented to them on the computer interface by moving the cursor with the aid of the head mounted IMU and select the target with the aid of the measured sEMG activity. The number of sentences will be arranged in consultation with our clinical collaborators so that the procedures can be completed within a reasonable timeframe.

Additional data acquisition during these experiments may include standard video recordings to assist in post-processing interpretation of results; and user-rated report of fatigue, effort, perceived benefit, ease of use or satisfaction through a brief Likert-type questionnaire.

Each session should require 1-3 hours over 1-2 sessions (depending on subject stamina) with rest periods provided at least every 10 minutes to avoid fatigue or lack of attentiveness.

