## Inclusion/Exclusion Criteria

# INDIVIDUALS WITH SPI

Inclusion criteria:

- Adults or Children; age> 8 y.o.

- Male or Female.

- All participants will be: (a) able to spell, (b) able to follow 2-3 step directions, (c) have functional vision sufficient to read 40 point text, and (d) have a motor impairment that requires the use of an alternative access strategy to communicate and/or use technology.

- Current or prospective AAC user with complex communication needs representing a broad spectrum of developmental and acquired SPI disabilities resulting from high spinal cord injury,

chronic Guillain-Barré syndrome, brain stem stroke, cerebral palsy, locked-in syndrome, among others

- Sufficient head control and voluntary facial muscle activation (on the basis of clinical evaluation by [name] and her team) to use the proposed wearable EMG/IMU sensor for the purposes of this study.

- Evidence of at least partial voluntary head movement in at least 2 degrees of freedom (Individual differences in providing controlled movements of the head in various degrees of freedom due to their disease or trauma is not only acceptable but desirable).

- Sufficient stamina and developmental maturity (on the basis of clinical evaluation by [name]) to attend to the approximately 1-hour protocol outlined in Aims 1 and 3 without excess fatigue or distraction.

- Availability for at least 3-4 testing sessions over the study period.

- No medical or safety restrictions of active head and neck movement (as determined by [name] in consultation with her clinical team).

- Clinical evidence of preserved cognition by a score of 0 or 1 on NIHSS Consciousness and Communication item.

- Ability to voluntarily blink eyes or raise eyebrows on command.

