## Exclusion criteria:

- Non-English speaker.

- Inability to follow simple instructions in English.

- Medical history of musculoskeletal conditions (arthritis, spondylosis, etc.) that severely limit head movement or causes pain on head movement.

- Restricted active or passive rotation of head and neck resulting from unstable vertebral, spinal cord, or nerve roots that places the subject at risk.

- Medical history of cardiac or respiratory complications, or similar disorders that would severely reduce stamina and/or place the subject at risk for conducting the different motor activities.

- Skin disorders that result in open lesions or hyper-sensitive/fragile skin on the forehead, preventing the use of medical-grade adhesive tapes to secure the sensors to the skin.

- Unable to provide informed consent in English.

CONTROLS

Inclusion Criteria:

- Adults and Children; >8 y.o.

- Male or Female.

- All participants will be: (a) able to spell, (b) able to follow 2-3 step directions, (c) have functional vision sufficient to read 40 point text.

- No history of communication disorders.

- No history of neurological disorders affecting speech or head movement.

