# **Alternatives to Participation**

This study does not involve medical diagnostics or treatments for which alternatives should be offered.

A series of signal acquisition and processing software will be developed to collect and analyze sEMG and IMU signals from wearable sensors to develop algorithms for person-centric AAC cursor control, which will then serve to train machine learning algorithms to achieve an individualized AAC keyboard interface. We will validate these developments to show that an individualized keyboard interface can provide improved communication performance compared to a generic (QWERTY) keyboard interface.

The analyses of sEMG and IMU data will be guided by our knowledge of sensor and signal processing solutions for human machine interfaces for preliminary prototype studies and early development of concepts rather than to prove efficacy. We purposely want to collect data from a diverse group to be able to capture a range of movement limitations so that we have a variety of potential "adaptations" the interface can make. A *single-subject design approach will therefore be adopted to evaluate these different, personalized adaptations.* For this reason, data analysis will be conducted across participants to compare individualized AAC device performance to generic (QWERTY) AAC device performance.

Data analysis will follow the U.S. Department of Education standards for single-subject statistical designs as each participant engages in a series of transcription (scripted) tasks to examine user-specific communication performance between our individualized AAC device and a generic (QWERTY) AAC device. Participant communication performance will collected within a single session for each device; the QWERTY keyboard will be analyzed in the second session (Day 2) to serve as a reference for communication performance (i.e., due to widespread familiarity in using the QWERTY keyboard for mobile device communication) once participants are familiar with the sEMG/IMU access method.

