The change in level (mean) and variability (standard deviation) of communication performance will be evaluated via metrics of information transfer rate (bits/min), movement time (sec), target selection accuracy (%), movement variability (unitless), and perceived usability for each participant across the two conditions. Average level and variability metrics will be reported for each metric to understand the effects of using an individualized keyboard interface compared to a generic one.

The output of these tasks will be a novel body-worn sensor-based access method, an access assessment test protocol and individualized keyboard interfaces that provide more accurate and accessible AAC over generic interfaces for individuals with SPI.

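### Does allowing one or two sessions according to stamina conflict with testing the QWERTY keyboard on Day 2?

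*Combined protocol and SAP*

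**What the plan says.** Three places in the combined protocol and SAP bear on the number of sessions.

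- **Protocol section:** "Each session should require 1-3 hours over 1-2 sessions (depending on subject stamina". The sentence is garbled, because a session cannot itself run over one or two sessions. It could mean a total for the study or a count for each experiment.
- **Data-analysis text under Alternatives to Participation:** performance is gathered in one session per device, and "the QWERTY keyboard will be analyzed in the second session (Day 2". The reason given is that QWERTY serves as the reference "once participants are familiar with the sEMG/IMU access method". No day is named for the individualized keyboard.
- **Inclusion criteria for individuals with SPI:** "Availability for at least 3-4 testing sessions over the study period", plus stamina for the "approximately 1-hour protocol outlined in Aims 1 and 3". The control inclusion list ends with "No history of neurological disorders affecting speech or head movement" and, like the control exclusion list, has no session item.

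The analysis compares the two keyboards within each participant and then summarizes: "Average level and variability metrics will be reported for each metric". Its stated purpose is "preliminary prototype studies and early development of concepts rather than to prove efficacy".

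**The concern.** QWERTY is the reference condition for the main comparison, and its Day 2 placement is reasoned: the sponsor wants participants to know the access method by then. The Protocol section lets the number of sessions vary with stamina and permits one. If staff took that as permission to finish someone in a single session, that participant would either have no QWERTY data or have it on the same day as the individualized keyboard, contrary to the data-analysis text. Some within-participant differences would then be same-day and others separate-day. They would be averaged together, with no planned record of which was which. Because stamina would drive the split, the mixing would not be random. The rest breaks and the optional fatigue rating do not record timing. Controls look most exposed, since no availability criterion covers them.

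**Working it through.** No sample size, power or error rate enters this point, so the check is a count of sessions.

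**Inputs**

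| Source | Sessions |
|---|---|
| Protocol section | 1 to 2 |
| Data-analysis text, Day 2 rule | at least 2, on separate days |
| SPI inclusion criterion (availability) | at least 3-4 |
| Control criteria | none stated |

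**Step 1: Protocol range against the Day 2 rule.** Shortfall = sessions needed − sessions allowed. Lower end: 2 − 1 = 1. Upper end: 2 − 2 = 0. The range 1 to 2 and the requirement of at least 2 have the value 2 in common, so the passages can both be obeyed.

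**Step 2: which passage governs.** The Protocol sentence is general logistics for everything described in that section. The Day 2 rule is specific to the keyboard comparison and has no stamina exception. The clause just before it assigns one session to each device. With two devices and QWERTY in the second session, the natural reading is two sessions for this comparison, although the document does not say so outright. On that reading the specific rule narrows the general range to its upper end. Finishing a participant in one session would be a departure from the plan, not an option within it.

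**Step 3: the two readings of the Protocol sentence.**

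- *Study total.* Against the SPI availability criterion, the smallest gap is 3 − 2 = 1 and the largest 4 − 1 = 3. This is not a true shortfall, because availability is a capacity and not a count of sessions held. Being available for 3 leaves room for 2.
- *Per experiment.* The documents give no number of experiments, so take k as assumed. For k = 2 the total is 2 × 1 = 2 to 2 × 2 = 4. For k = 3 it is 3 × 1 = 3 to 3 × 2 = 6. Both ranges contain 3-4. The Specific Aims section describes a series of experiments, and the SPI stamina criterion refers to an hour-long protocol under two named aims, so this reading is plausible. If each keyboard counts as its own experiment (k = 2), even the lower end gives two sessions. If the comparison is one experiment, Step 2 applies.

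**Step 4: who could be affected.** For SPI participants, two sessions are feasible by criterion. For controls, the data-analysis text does not say that they enter the individualized-versus-QWERTY averages, and it frames the output as serving individuals with SPI. Mixed timing in the averages would need both a departure from the Day 2 rule and, if it came from controls, their inclusion in those averages.

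**Step 5: size of any effect.** The documents give no practice effect, between-day variation or number of one-session participants. Neither size nor direction can be computed.

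**The case for a change.** The strongest case for a change is that three minimum counts (1, 2 and 3) stand in one document with nothing to connect them, that the reference condition depends on one of them, and that clearer wording would cost a sentence or two. The availability criterion states willingness to attend, not sessions held, and it leaves controls out. The same text also speaks of validating better performance than QWERTY, so the timing of the reference is not trivial.

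Part of this stands. The Protocol sentence is unclear, and nothing says how its count relates to the other two. Anyone next editing the document could usefully reconcile the three places; I take no position on what the schedule should be. What does not stand is the step from loose wording to a flaw in the comparison. That step needs staff to let a general range override a specific rule. Recording and displaying same-day status would provide for an event that the plan does not foresee. If it did occur, the individual contrasts would still exist, because performance is evaluated participant by participant before averaging.

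**Conclusion.** No change to the plan is called for. The gap is one of wording, and staff and analysts fill it by following the more specific instruction. At most the Protocol range falls one session short of the Day 2 rule, and at its upper end it does not fall short at all. Followed as written, the data-analysis text gives each participant in the comparison a Day 2 QWERTY session. No stated figure, analysis or decision rule would alter if the sentence were tidied, and the results are descriptive summaries in early development work.

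This rests on two assumptions: that one session per device with QWERTY second means two sessions on separate days, and that the Day 2 rule prevails over the general range. The conclusion concerns only whether the session counts conflict. It does not judge the fixed placement of QWERTY on Day 2 as a design choice.
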